
Investigational Plan:
	
Study 1 (bDMARD-IR AS) is comprised of a 35-day Screening Period; a 14-week randomized, double-blind, parallel-group, placebo-controlled period (the Double-Blind Period); a 90-week open-label, long-term extension period (the Open-Label Extension Period); and a 30-day Follow-Up Visit (F/U Visit).
 
Study 2 (nr-axSpA) is comprised of a 35-day Screening Period; a 52-week randomized, double-blind, parallel-group, placebo-controlled period (the Double-Blind Period); a 52-week open-label, long-term extension period (the Open-Label Extension Period); and a 30-day F/U Visit.

	
In the Double-Blind Period for both studies, subjects will be randomized in a 1:1 ratio to 1 of 2 treatment groups:
 
Study 1 (bDMARD-IR AS):
 
 • Group 1: upadacitinib 15 mg QD (N = 193) • Group 2: placebo QD (N = 193) 
Study 2 (nr-axSpA):
 
 • Group 1: upadacitinib 15 mg QD (N = 152) • Group 2: placebo QD (N = 152) 
Subjects in the placebo group will be switched to upadacitinib 15 mg QD at Week 14 in the Open-Label Extension Period for Study 1 (bDMARD-IR AS) and Week 52 in the Open-Label Extension Period for Study 2 (nr-axSpA).
 
Remission-Withdrawal Period:
 
 • Subjects with an ASDAS (C-reactive protein [CRP]) < 1.3 at Week 104 and an ASDAS (CRP) < 2.1 at Week 88 will be eligible for the open-label remission-withdrawal period. Subjects will be followed and assessed for potential flare through Week 152. Subjects who flare during this period (flare defined as ASDAS [CRP] ≥ 2.1 at 2 consecutive visits, which are at least 2 weeks apart, or ASDAS [CRP] > 3.5 at one visit) will be eligible to receive open-label upadacitinib 15 mg QD for 24 weeks (re-treatment) from the timepoint of flare. Subjects who do not flare through Week 152 during the withdrawal period, will have reached the end of the study. • Subjects not eligible for the withdrawal period will have reached the end of the study after the 30 day follow-up visit. 
For subjects in Japan only: Upon marketing approval of upadacitinib for the treatment of nr-axSpA in Japan, M19-944 Study 1 and Study 2 will be changed from Phase 3 studies to post-marketing clinical studies in Japan.

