3.4 Additional Endpoints

Study 1 (bDMARD-IR AS):

Additional endpoints are the following measurements assessed at scheduled time points other than those specified for the primary and secondary endpoints:

Binary variables:

- ASAS20 response;
- ASAS40 response;
- BASDAI 50 response;
- ASAS PR;
- ASDAS ID (ASDAS score < 1.3);
- ASDAS LDA (ASDAS score < 2.1);
- ASDAS Major Improvement (a change from Baseline of ≤ -2.0);
- ASDAS Clinically Important Improvement (a change from Baseline of ≤ -1.1);
- Discontinuation of opioids among subjects with opioid use at Baseline.

Change from Baseline in:

- ASAS HI;
- ASDAS;
- ASQoL;
- BASDAI and BASDAI components including mean of question 5 and 6 of the BASDAI;
- BASFI;
- BASMI_{lin};
- High sensitivity C-reactive protein (hsCRP);
- EuroQoL-5D-5L (EQ-5D-5L);
- Functional Assessment of Chronic Illness Therapy-Fatigue (FACIT-F);
- MASES;
- Modified Stoke Ankylosing Spondylitis Spine Score (mSASSS) with conventional radiograph;
- MRI SPARCC score of SI joints;
- MRI SPARCC score of spine;

- Patient's Assessment of Total Back Pain (Total Back Pain);
- Patient's Assessment of Nocturnal Back Pain (Nocturnal Back Pain);
- Patient's Global Assessment of Pain;
- Physician's Global Assessment of Disease Activity (PGA);
- Patient's Global Assessment of Disease Activity (PtGA);
- 36-Item Short Form Health Survey (SF-36);
- Tender joint count (TJC) and swollen joint count (SJC);
- Work Productivity and Activity Impairment (WPAI);
- NSAID score;
- Physical Activity Assessment (step count, physical activity, and spinal range of motion tasks) as measured by a wearable device (except in countries where the digital health technology device is not available or is not allowed to be used in the study by the local regulatory authority).

Additional endpoint relating to the assessment of disease flare for subjects on upadacitinib treatment who achieve an ASDAS C-reactive protein (CRP) < 1.3 at Week 52 and an ASDAS (CRP) < 2.1 at Week 40:

- Time to flare during Week 52 to Week 104

Study 2 (nr-axSpA):

Additional endpoints are the following measurements assessed at scheduled time points other than those specified for the primary and secondary endpoints:

Binary variables:

- ASAS20 response;
- ASAS40 response;
- BASDAI 50 response;
- ASAS PR;
- ASDAS ID (ASDAS score < 1.3);
- ASDAS LDA (ASDAS score < 2.1);
- ASDAS Major Improvement (a change from Baseline of ≤ -2.0);

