3.0 Endpoints for Remission-Withdrawal Study

3.1 Endpoints for Withdrawal Period

During the Withdrawal Period, the time-to-flare endpoint is defined as follows:

- Flare event criterion is defined as ASDAS (CRP) score > 2.1 at two consecutive visits, which are at least 2 weeks apart, or ASDAS (CRP) score > 3.5 at one visit
- Time-to-flare is defined as the number of days between the first day of treatment withdrawal and the day on which the criterion is met.

Additional endpoints during the Withdrawal Period include the following measurements assessed at scheduled time points in the Withdrawal Period:

Binary variables:

- Assessment of SpondyloArthritis international Society (ASAS) 20 response*;
- ASAS40 response*

- Bath Ankylosing Spondylitis Disease Activity Index (BASDAI) 50 response* ;
- ASAS Partial Remission (PR);
- Inactive Disease based on ASDAS(CRP) (ASDAS score < 1.3)
- Low Disease Activity based on ASDAS(CRP) (ASDAS score < 2.1);
- Major Improvement based on ASDAS(CRP) (a change from Original Baseline of ≤ 2.0);
- Clinically Important Improvement based on ASDAS(CRP) (a change from Original Baseline of ≤ 1.1);

* *Relative to Original Baseline.*

Change from Original Baseline in:

- ASDAS(CRP) and components;
- BASDAI and BASDAI components including mean of question 5 and 6 of the BASDAI (Score 0 - 10);
- Bath Ankylosing Spondylitis Functional Index (BASFI) (Score 0 - 10);
- Linear Bath Ankylosing Spondylitis Metrology Index (BASMI_{lin});
- Maastricht Ankylosing Spondylitis Enthesitis Score (MASES) for subjects with baseline enthesitis (MASES > 0);
- Patient's Assessment of Total Back Pain NRS score 0 - 10;
- Patient's Assessment of Nocturnal Back Pain NRS score 0 - 10;
- Patient's Global Assessment of Pain NRS score 0 - 10;
- Physician's Global Assessment of Disease Activity (PGA) Numeric Rating Scale (NRS) score 0 - 10;
- Patient's Global Assessment of Disease Activity (PtGA) NRS score 0 - 10;
- Tender joint count (TJC68) and swollen joint count (SJC66);
- ASAS Health Index (HI).

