3.2 Endpoints for Re-Treatment Period

During the Re-treatment Period, endpoints include the following measurements assessed at scheduled time points in Re-treatment Period:

Binary variables:

- ASAS20 response* ;
- ASAS40 response* ;
- BASDAI 50 response* ;
- ASAS PR;
- Inactive Disease based on ASDAS(CRP) (ASDAS score < 1.3)
- Low Disease Activity based on ASDAS(CRP) (ASDAS score < 2.1);
- Major Improvement based on ASDAS(CRP) (a change from Re-treatment Baseline of ≤ 2.0);
- Clinically Important Improvement based on ASDAS(CRP) (a change from Re-treatment Baseline of ≤ 1.1);

* *Relative to Re treatment Baseline.*

Change from Re-treatment Baseline in:

- ASDAS(CRP) and components;
- BASDAI and BASDAI components including mean of question 5 and 6 of the BASDAI (Score 0 - 10);
- BASFI (Score 0 - 10);
- BASMI_{lin};
- MASES for subjects with baseline enthesitis (MASES > 0);
- Patient's Assessment of Total Back Pain NRS score 0 - 10;
- Patient's Assessment of Nocturnal Back Pain NRS score 0 - 10;
- Patient's Global Assessment of Pain NRS score 0 - 10;
- Physician's Global Assessment of Disease Activity (PGA) NRS score 0 - 10;
- Patient's Global Assessment of Disease Activity (PtGA) NRS score 0 - 10;

- Tender joint count (TJC68) and swollen joint count (SJC66);
- ASAS HI.

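### All four ASDAS improvement definitions in the SAP lack the protocol's minus sign, so read literally they count no change, and some worsening, as response

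*SAP*

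**What the plan says.** The SAP for the Remission-Withdrawal Period lists the two responses among the binary variables of each period.

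- Withdrawal Period (SAP 3.1): "Major Improvement based on ASDAS(CRP) (a change from Original Baseline of ≤ 2.0" and "Clinically Important Improvement based on ASDAS(CRP) (a change from Original Baseline of ≤ 1.1".
- Re-treatment Period (SAP 3.2): "Major Improvement based on ASDAS(CRP) (a change from Re-treatment Baseline of ≤ 2.0" and "Clinically Important Improvement based on ASDAS(CRP) (a change from Re-treatment Baseline of ≤ 1.1".

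Protocol section 3.4 defines them, for Study 1 and again for Study 2, as "ASDAS Major Improvement (a change from Baseline of ≤ -2.0" and "ASDAS Clinically Important Improvement (a change from Baseline of ≤ -1.1". Its list for the Remission-Withdrawal Period names the same two responses without repeating the thresholds.

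Three handling rules bear on the effect. SAP 8.0 makes a re-treated subject a non-responder at all later Withdrawal Period visits. SAP 9.2.1.2 makes missing Withdrawal Period data non-response. SAP 9.3.1.1 imputes nothing in the Re-treatment Period. SAP 9.1 and 13.0 state that no testing is done.

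**The concern.** A lower ASDAS is better, so improvement is a negative change. A threshold of +2.0 or +1.1 admits every subject who improves by any amount, every subject who does not change, and every subject who worsens by no more than that amount. The SAP is the document from which the tables are programmed. If its text were followed as it stands, four listed endpoints would no longer measure improvement, and they would not match the protocol endpoints of the same name.

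**Working it through.** **Inputs.** Thresholds: -2.0 and -1.1 (protocol 3.4); 2.0 and 1.1 (SAP 3.1 and 3.2). Flare, from the protocol synopsis: "ASDAS [CRP] ≥ 2.1 at 2 consecutive visits, which are at least 2 weeks apart, or ASDAS [CRP] > 3.5 at one visit". Inactive disease, from SAP 3.2: "Inactive Disease based on ASDAS(CRP) (ASDAS score < 1.3". The plan gives no figure to reproduce; the check is threshold arithmetic.

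**Step 1: the order of the two responses.** With the protocol's signs, a change of ≤ -2.0 is also ≤ -1.1, so every Major responder is a Clinically Important responder. With the SAP's signs this reverses: a change of ≤ 1.1 is also ≤ 2.0, so Major Improvement becomes the easier of the two. The literal rule therefore contradicts the endpoint names.

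**Step 2: Re-treatment Period.** Let B be the Re-treatment Baseline ASDAS. A responder has ASDAS ≤ B + 2.0 or ≤ B + 1.1 on the SAP text, and ≤ B - 2.0 or ≤ B - 1.1 on the protocol's thresholds.

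| B | SAP, Major | SAP, Clinically Important | Protocol sign, Major | Protocol sign, Clinically Important |
|---|---|---|---|---|
| 2.1 | ≤ 4.1 | ≤ 3.2 | ≤ 0.1 | ≤ 1.0 |
| 2.5 | ≤ 4.5 | ≤ 3.6 | ≤ 0.5 | ≤ 1.4 |
| 3.0 | ≤ 5.0 | ≤ 4.1 | ≤ 1.0 | ≤ 1.9 |
| 3.5 | ≤ 5.5 | ≤ 4.6 | ≤ 1.5 | ≤ 2.4 |

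On the SAP text, a non-responder must rise by more than 2.0 or 1.1 above the re-treatment starting value. If few subjects do so after restarting drug (an assumption), the as-observed rates are close to 100%.

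**Step 3: Withdrawal Period.** Let O be the Original Baseline ASDAS. A subject who has not met the single-visit flare rule has ASDAS ≤ 3.5. On the SAP text every such value is a Major response if O ≥ 3.5 - 2.0 = 1.5, and a Clinically Important response if O ≥ 3.5 - 1.1 = 2.4. The protocol sets no minimum ASDAS at entry. It requires BASDAI ≥ 4 and Total Back Pain ≥ 4, so original baselines above these values are a reasonable assumption, not a stated fact. On that assumption, nearly every subject who is observed and not yet re-treated is a responder. What then moves the rate is re-treatment and missing data.

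**Step 4: what the protocol's sign implies in the Re-treatment Period.** Major Improvement is stricter than inactive disease when B - 2.0 < 1.3, that is B < 3.3. Clinically Important Improvement is stricter when B - 1.1 < 1.3, that is B < 2.4. For example, a subject going from 2.3 to 1.25 reaches inactive disease with a change of only -1.05.

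In the band from 2.1 to 3.5 (width 1.4), the stricter zone is (3.3 - 2.1)/1.4 = 86% of the width for Major and (2.4 - 2.1)/1.4 = 21% for Clinically Important. These are shares of an interval, not of subjects, because the documents give no distribution of ASDAS at flare.

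To show a range, assume B in the band is uniform or triangular with its mode at either end, and that 0 to 50% of re-treated subjects start above 3.5, where neither response is stricter.

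- Major: lowest 0.5 × 0.857² = 37%; highest 1 - (1 - 0.857)² = 98%.
- Clinically Important: lowest 0.5 × 0.214² = 2%; highest 1 - (1 - 0.214)² = 38%.

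SAP 8.0 also foresees re-treatment without a flare, so some values of B could lie below 2.1, outside this illustration.

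**The case against.** **The sign may be missing only from the extracted text.** This is the strongest objection, and it cannot be excluded. The SAP text loses hyphens elsewhere, including in the footnote just under the binary list in section 3.2, and it loses hyphens and equals signs in the Figure 1 legend. No other negative number appears in the SAP to show whether a leading minus survives. Against this, the visible losses sit mainly in footnotes and legends. The affected lines are body bullets, and those in section 3.2 keep the hyphen in Re-treatment on the same line. Section 3.1 also has a flare cut-off of > 2.1, where SAP 2.2 and the protocol have ≥ 2.1; a dropped hyphen does not explain that, and those passages need reconciling in their own right. What stands is that the point needs a source check before it is called an error in the SAP.

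**The intent is obvious.** The names and the protocol do make it clear, and a careful programmer would probably use the negative thresholds. That lowers the risk but does not remove the need for the SAP to state the rule correctly.

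**Stronger readings that the documents do not support.**

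- A reader might infer rates near 100% in both periods. In the Withdrawal Period the non-responder rules for re-treated and missing subjects pull the rate down.
- A reader might infer that, with the sign restored, the re-treatment versions conflict with the inactive-disease cut-off. A change endpoint and a state endpoint need not be nested. Measuring from Re-treatment Baseline is a deliberate choice made in protocol 3.4 and 7.3 and in SAP 2.2 and 3.2, and inactive disease and low disease activity are reported alongside.
- A reader might infer that many re-treated subjects are affected. Without a distribution of ASDAS at flare, the number is unknown.
- A reader might extend the point to the Week 14 or Week 52 analyses. This SAP covers only the Remission-Withdrawal Period; Study 1 and Study 2 have separate SAPs.

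**Conclusion.** The point holds for the SAP text, subject to a check of the source. Four definitions carry the wrong sign relative to the protocol, and taken literally they reverse the meaning of the two endpoints in both periods. The size of the effect rests on two assumptions: few subjects worsen by more than 1.1 or 2.0 after restarting drug, and original baselines are mostly at or above 1.5 and 2.4. Severity is moderate: these are additional, descriptive endpoints, no test or error rate depends on them, and other ASDAS measures are reported beside them. The relation between the restored re-treatment thresholds and inactive disease is a matter of interpretation, not a defect.

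**What to change.** 1. Check the source SAP for a lost character at the four places. If the minus sign is present, nothing needs changing.
2. If it is absent, restore ≤ -2.0 and ≤ -1.1 in sections 3.1 and 3.2, and confirm that the table programs use the negative thresholds. The cost is a wording correction; no new data are needed.
3. Optional: show the distribution of Re-treatment Baseline ASDAS beside the two re-treatment rates, with the counts below 2.4 and below 3.3. This is one descriptive table from data already collected. It keeps the protocol's reference baseline and avoids rates restricted to subjects with high flare values, which would have smaller denominators and be open to regression to the mean.

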3.2 Endpoints for Re-Treatment Period

During the Re-treatment Period, endpoints include the following measurements assessed at scheduled time points in Re-treatment Period:

Binary variables:

- ASAS20 response* ;
- ASAS40 response* ;
- BASDAI 50 response* ;
- ASAS PR;
- Inactive Disease based on ASDAS(CRP) (ASDAS score < 1.3)
- Low Disease Activity based on ASDAS(CRP) (ASDAS score < 2.1);
- Major Improvement based on ASDAS(CRP) (a change from Re-treatment Baseline of ≤ 2.0);
- Clinically Important Improvement based on ASDAS(CRP) (a change from Re-treatment Baseline of ≤ 1.1);

* *Relative to Re treatment Baseline.*

Change from Re-treatment Baseline in:

- ASDAS(CRP) and components;
- BASDAI and BASDAI components including mean of question 5 and 6 of the BASDAI (Score 0 - 10);
- BASFI (Score 0 - 10);
- BASMI_{lin};
- MASES for subjects with baseline enthesitis (MASES > 0);
- Patient's Assessment of Total Back Pain NRS score 0 - 10;
- Patient's Assessment of Nocturnal Back Pain NRS score 0 - 10;
- Patient's Global Assessment of Pain NRS score 0 - 10;
- Physician's Global Assessment of Disease Activity (PGA) NRS score 0 - 10;
- Patient's Global Assessment of Disease Activity (PtGA) NRS score 0 - 10;

- Tender joint count (TJC68) and swollen joint count (SJC66);
- ASAS HI.

3.3 Safety Endpoints

The following safety evaluations will be performed for each period in the Remission-Withdrawal study as well as Open-Label Extension Period: adverse events (AEs), serious adverse events (SAEs), AE of special interest (AESI), AEs leading to discontinuation, vital signs, laboratory tests, and physical examination findings.

4.0 Analysis Populations

The Analysis Populations are defined in [Table 1](#) and [Table 2](#) below.

[figure not shown]
Table 1. Analysis Population for Efficacy Analyses

Analyses Population	Definition	Analyses Group
Withdrawal Analysis Set (WAS)	All subjects who entered the Remission-Withdrawal Period	Off Upadacitinib Treatment
Re-treatment Analysis Set (RAS)	All subjects who entered the Remission-Withdrawal Period and received at least one dose of Upadacitinib re-treatment in the Remission-Withdrawal Period	Upadacitinib 15 mg Re-treatment in RW

Table 2. Analysis Population for Safety Analyses

[figure not shown]
Analyses Population	Definition	Analyses Group	Data for Analyses
UPA reinitiation	All subjects who received at least one dose of reinitiated upadacitinib	Upadacitinib 15 mg	Safety data after reinitiation of upadacitinib (i.e., F+G+H as shown in Figure 2) will be included in safety analyses for summary of safety after reinitiating upadacitinib.
ALL UPA	All subjects who received at least one dose of upadacitinib in M19-944.	Any Upadacitinib 15 mg	Safety data under upadacitinib exposure in M19-944 (i.e., A+C+E+F+G+H in Figure 3) will be included in safety analyses for the totality of upadacitinib safety in M19-944.

Figure 2. Study Drug Exposure for Reinitiated Upadacitinib (UPA reinitiation)

Study 1 includes 14 week double blind placebo controlled period with 90 week open label period. Study 2 includes 52 week double blind placebo controlled period with 52 week open label period.

Figure 3. Study Drug Exposure for All Upadacitinib (ALL UPA)

Study 1 includes 14 week double blind placebo controlled period with 90 week open label period. Study 2 includes 52 week double blind placebo controlled period with 52 week open label period.

5.0 Subject Disposition

A summary of subject accountability will be provided where the number of subjects in each of the following categories will be summarized for overall and for Study 1 and Study 2 respectively:

- Subjects enrolled in the Withdrawal Period
- Subjects who completed Withdrawal Period
- Subjects who prematurely discontinued study during the Withdrawal Period
- Subjects who entered Re-treatment Period
- Subjects who completed Re-treatment Period
- Subjects who prematurely discontinued study drug during Re-treatment Period
- Subjects who entered Open-Label Extension Period

6.0 Study Treatment Duration and Compliance

The duration of treatment will be summarized for the UPA reinitiation and ALL UPA populations.

Study Drug Duration (in Days) (UPA reinitiation):

- Duration of Upadacitinib 15 mg: Last dose date of reinitiated upadacitinib 15 mg – first dose date of reinitiated upadacitinib 15 mg + 1

Study Drug Duration (in Days) (ALL UPA):

- Duration of Any Upadacitinib 15 mg: Last dose date of upadacitinib 15 mg – first dose date of upadacitinib 15 mg + 1, excluding the duration of withdrawal

The duration of exposure to study drug will be summarized as specified above, with the number of subjects, mean, standard deviation, median, minimum and maximum values. In addition, the number and percentage of subjects exposed to study drug will be summarized for the following cumulative duration intervals:

- ≥ 2 weeks
- ≥ 4 weeks
- ≥ 12 weeks
- ≥ 24 weeks
- ≥ 9 months
- ≥ 12 months
- ≥ 18 months
- ≥ 2 years
- ≥ 2.5 years
- ≥ 3 years
- ≥ 3.5 years
- ≥ 4 years

Study drug compliance will not be summarized for the Remission-Withdrawal Study.

7.0 Demographics, Baseline Characteristics, Medical History, and Prior/Concomitant Medications

Demographics, baseline or disease characteristics and medical history will be summarized relative to the start of the original study (Study 1 or Study 2), and prior and concomitant medications will be summarized relative to the start of the Remission-Withdrawal Period overall and for Study 1 and Study 2 subgroups. Categorical variables will be summarized with the number and percentage of subjects. Continuous variables will be summarized with descriptive statistics (number of non-missing observations, mean and standard deviation, median, minimum and maximum).

7.1 Demographics and Baseline Characteristics

Main Demographic and Original Baseline Characteristics

- Sex (male, female)
- Age (years)
- Age Categories (< 40, ≥ 40 and < 65, ≥ 65 years)
- Race (White, Non-White)
- Geographic Region (North America, South/Central America, Western Europe, Eastern Europe, Asia, Other)
- Weight (kg)
- Weight Categories (< 60, ≥ 60 and < 80 kg, ≥ 80 kg)
- Height (cm)
- Body Mass Index (BMI) (kg/m²)
- Body Mass Index (BMI) Category (kg/m²) (BMI < 25, BMI ≥ 25)

Axial SpA Medical History and Characteristics at Original Baseline

- Duration (years) of Axial SpA symptoms
- Duration (years) since Axial SpA diagnosis
- Duration since Axial SpA diagnosis categories (< 5 years, ≥ 5 - 10 years, ≥ 10 years)

- Duration of Axial SpA symptoms categories (< 5 years, ≥ 5 - 10 years, ≥ 10 years)
- HLA-B27 (positive, negative)
- Oral Corticosteroids use at baseline
- csDMARDs use at baseline
- Opioid use at baseline
- NSAID score at baseline

Table 3. ASAS and/or ASDAS Components at Original Baseline

ASAS only components	
 ● Patient's assessment of total back pain (NRS score 0 - 10) ● Function – Represented by the BASFI (NRS score 0 - 10) ● Inflammation – (mean of items 5 and 6 of the BASDAI NRS score 0 – 10)
ASDAS only components	
 ● Patient's assessment of back pain (BASDAI Question 2 NRS score 0 – 10) ● Peripheral pain/swelling (BASDAI Question 3 NRS score 0 – 10) ● High sensitivity C-reactive protein (hs-CRP) in mg/L ● Erythrocyte sedimentation rate (ESR) (mm/hr) ● Duration of morning stiffness (BASDAI Question 6 NRS score 0 – 10)
Components for both ASAS and ASDAS	
 ● Patient global assessment of disease activity (NRS score 0 – 10)

Other Original Baseline Axial SpA Disease Characteristics

- ASDAS (CRP)
- ASDAS(CRP) categories (ASDAS(CRP) > 3.5 vs ≤ 3.5)
- Physician's Global Assessment of Disease Activity (NRS score 0 - 10)
- BASMI_{lin}
- MASES for subjects with baseline enthesitis (MASES > 0)
- Presence of enthesitis (MASES > 0)
- Tender Joint Count (TJC68)
- Swollen Joint Count (SJC66)
- High Sensitivity C-reactive Protein (hsCRP) (mg/L) at Screening
- Screening hsCRP levels (> ULN vs ≤ ULN, > 5mg/L vs ≤ 5mg/L)

- MRI (SI joints) inflammation at screening (positive vs negative)*
- MRI+/hsCRP > ULN, MRI+/hsCRP ≤ ULN, and MRI-/hsCRP > ULN at screening*
- Prior failed bDMARDs (yes or no)

* For Study 2 only.

Patient Reported Outcomes and Measures at Original Baseline

- BASDAI (Score 0-10)
- ASAS HI
- Patient's Assessment of Nocturnal Back Pain (NRS score 0 - 10)
- Patient's Global Assessment of Pain (NRS score 0 - 10)

